5. METHODS AND PROCEDURES

5.1. STUDY PROCEDURES

The majority of study procedures will relate to their course of radiation therapy. The dose, scheduling and duration of radiation therapy will be determined by the attending radiation oncologist and are outside of the purview of this study. All study visits will take place at the time of scheduled radiation therapy sessions and will not involve additional travel.

To ensure appropriate safety precautions when conducting in-person study procedures, the process for conducting in-person visits outlined in the Guidance for Human Subject Research will be followed.

• Study personnel will keep track of all patients that are eligible for the study, all patients approached about the study, and the outcome of that discussion (Declined participation or Consented). For patients that declined participation, study personnel will indicate the reason for decline. All of this information will be entered into the electronic REDCap Screening Log for the study.

• Baseline Visit (after consent):

- O Study personnel will obtain demographic and lifestyle information from the subject to complete the OnStudy Data Form. This information will include: age, gender, race, ethnicity, marital status, smoking status, alcohol use, prescription opioid use, and breast size (i.e., bra size), and if they had breast reconstructive surgery before radiation therapy. This form can be completed electronically in REDCap or on paper and then entered into REDCap.
- The subject will complete a Study Reimbursement Form and W9 to receive their payment at the end of the study for participation.
- O Study personnel will take baseline digital photographs of skin in radiation treatment area (i.e., where the Silverlon® will be applied).
- o The subject will be asked to complete a paper questionnaire, Dermatology Life

Page 15 of 41 RSRB STUDY00004587 Version Date: 09/14/2021 NCT04238728

- Quality Index (DLQI). This will provide baseline quality of life and symptoms for the subject prior to the start of RT and Silverlon® Dressing. Study personnel will electronically enter the data from the form into REDCap for secure storage in the study database.

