Page 17 of 41 RSRB STUDY00004587 Version Date: 09/14/2021 NCT04238728

- Mid-Study Visit: This visit will occur at the subject's scheduled mid-treatment clinic visit with their radiation oncologist. Study personnel will meet with the subject with or after the radiation oncologist at this visit. Subjects will be reminded of this study visit at the phone call the previous week.
 - The radiation oncologist will clinically assess the radiation-induced skin reaction in the breast area that Silverlon® dressing was applied. The radiation oncologist will rate the skin using the RTOG scale and the RISRAS-Healthcare Professional Assessment Scale. These ratings will be completed electronically in on a tablet (in REDCap).
 - O The subject will complete two surveys that contain: **Dermatology Life Quality Index (DLQI) and RISRAS-Patient Symptom Scale.** The subjects will be asked to complete these forms by focusing on the whole breast to which the Silverlon® dressing has been applied. These surveys will be completed electronically on a tablet (in REDCap).
 - o **Digital photographs** of the skin in the radiation treatment area (where the Silverlon® dressing has been applied) will be taken.
 - Study personnel will also ask the subject: 1) if they are having any adverse reactions to wearing Silverlon®; 2) if they are wearing Silverlon® while sleeping; 3) having any discomfort while wearing Silverlon®; and 4) if they feel Silverlon® is helping their skin. This information will be entered electronically into the Questions Log.
 - Study personnel will also complete the Weekly AE/Chart Review Source Doc at this visit to document any adverse reactions, skin changes, and/or radiation treatment changes.
 - This visit is estimated to involve 10 minutes of less of the patient's time.

Page 18 of 41 RSRB STUDY00004587 Version Date: 09/14/2021 NCT04238728

- Completion of Radiation Therapy Visit (EndRT Visit): This visit will be scheduled with the subject at their scheduled last radiation treatment. Study personnel will meet with the subject with or after the radiation oncologist at this visit. Subjects will be reminded of this study visit at the phone call the previous week.

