	decreased	moist	pitting edema		
	sweating	desquamation			

Page 23 of 41 RSRB STUDY00004587 Version Date: 09/14/2021 NCT04238728 Radiation Induced Skin Reaction Assessment Scale (RISRAS): This scoring system contains both a healthcare professions assessment scale and a patient symptom scale (23). The healthcare professional assessment scale individually scores the extent and severity of erythema, dry desquamation, moist desquamation, and necrosis using a 5-point scale from 0 to 4. Erythema is rated based on the degree of color change. Dry desquamation, moist desquamation, and necrosis are rated based on the percentage of the treatment area affected by that particular reaction. The patient component focuses on skin tenderness, itching, burning, and functional activity using a 4-point scale from 1 to 4. The Healthcare Professional Assessment Scale scores and the Patient Symptom Scale scores are added together for a total skin reaction score. The higher the score, the worse the skin reaction. The Healthcare Professional Assessment Scale will be completed by the radiation oncologist in person at Mid-Study Visit, EndRT Visit, and 2-Week Post-RT Visit. The Patient Symptom Scale will be completed by the subject at the Mid-Study Visit, EndRT Visit, and 2-Week Post-RT Visit. Study personnel will enter the data from the completed forms into REDCap.

HEALTHCARE PROFESSIONAL ASSESSMENT SCALE

HEREITICHE THOI ESSIONAL HESSESSANETT SCHEE						
	0	1	2	3	4	
Erythema (E)	Normal Skin	Dusky pink	Dull red	Brilliant red	Deep red/purple	
Dry Desquamation (DD)	Normal Skin	<25%	>25-50%	>50-75%	>75-100%	
Moist Desquamation (MD)	Normal Skin	<25%	>25-50%	>50-75%	>75-100%	
Necrosis (N)	Normal Skin	<25%	>25-50%	>50-75%	>75-100%	

PATIENT SYMPTOM SCALE

	Not at all	A little	Quite a bit	Very much
Tenderness,				
Discomfort, or	1	2	3	4
Pain?				
Itch?	1	2	3	4
Burning sensation?	1	2	3	4
Skin reaction				
interfered with day	1	2	3	4
to day activities?				

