13.2. Statistical Analyses

This is a safety study to determine Silverlon® dressing indication for radiation dermatitis. Descriptive statistics will be used to describe the study subject population. The primary analyses will evaluate the number of adverse events or reactions reported (if any) at the breast irradiation site where the Silverlon® dressing was applied. The primary analyses will be conducted on 30 fully evaluable subjects (i.e., 30 subjects that fully complete the study) and on all subjects that initiated treatment with Silverlon® dressing in an intent to treat analysis (see section 13.1). For a safety study, it is important to obtain the overall adverse event rate for all subjects that initiated treatment and all subjects who fully completed the study.

The secondary analyses will evaluate the compliance rates for the Silverlon® Dressing during RT and post RT. Compliance will be on the number of days during RT and post-RT that the dressing was worn. We expect compliance rate to be 97% (8). Additionally, we will evaluate the percentage of subjects that removed the dressing for sleeping. Subjects are asked to wear the dressing during sleep and only remove the dressing for RT sessions, showering/bathing, or swimming. Furthermore, we will calculate the number of hours during a day that the dressing was not worn summing the time between removal and application of the dressing each day.

Page 34 of 41 Version Date: 09/14/2021 Compliance will be evaluated in the 30 fully evaluable subjects. Although we can and will evaluate compliance in all subjects that initiated treatment, these analyses will not provide a complete picture of compliance due to early termination of study procedures. Furthermore, the secondary analyses will also evaluate withdrawal rates due to the Silverlon® dressing in all subjects who initiated treatment. We expect less than 6 subjects to withdraw due to the Silverlon® dressing. The exploratory analyses will assess trends in radiation dermatitis severity (i.e., RTOG and RISRAS) and quality of life (DLQI) during the course of the study. These analyses will also be able to evaluate changes in skin symptoms experience by the patient based on the RISRAS-Patient Symptom Scale during RT.

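### The RISRAS-Patient Symptom Scale is first scored at mid-treatment, so the planned symptom changes miss onset and pre-RT symptoms cannot be separated from dermatitis in its levels

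*Combined protocol and SAP*

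**What the plan says.** Section 13.2 describes the exploratory work in two steps. First, "The exploratory analyses will assess trends in radiation dermatitis severity (i.e., RTOG and RISRAS) and quality of life (DLQI") over the study. Second, the analyses are to "evaluate changes in skin symptoms experience by the patient based on the RISRAS-Patient Symptom Scale during RT". No test, model or summary measure is given.

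Section 5.3 fixes the timing: "The Patient Symptom Scale will be completed by the subject at the Mid-Study Visit, EndRT Visit, and 2-Week Post-RT Visit". The visit descriptions in section 5.1 and the section 15 schedule agree with it. At the Baseline Visit the only patient-reported instrument is the DLQI, of which section 5.1 says "This will provide baseline quality of life and symptoms for the subject prior to the start of RT and Silverlon® Dressing". The skin itself is recorded before treatment by photograph only: "Study personnel will take baseline digital photographs of skin in radiation treatment area".

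On content, section 5.3 states: "The patient component focuses on skin tenderness, itching, burning, and functional activity using a 4-point scale from 1 to 4". The patient score is then added to the professional score to give a total, which is read as the severity of the skin reaction.

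**The concern.** The exploratory objective in section 1.3 is to follow dermatitis severity and quality of life while the dressing is worn, throughout RT and afterwards. The dressing goes on from the first day of RT, and section 2.1 states that there is no control or placebo group. A subject's own state before RT is then the only reference available, and for the patient symptom scale it is not recorded.

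Two things follow. The change that section 13.2 promises can start only at mid-treatment, after part of the reaction may already have developed. And section 3.5 allows lumpectomy or mastectomy before RT, so some women may start with tenderness, itch or burning in the breast. Without a pre-RT score, those points remain in every later level of the scale and in the RISRAS total.

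At stake is how the exploratory symptom results read in a single-arm study whose composite data are meant to support an application for a radiation dermatitis indication. The primary safety endpoint and the secondary endpoints (compliance, withdrawal) do not use this scale.

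**Working it through.** The plan gives no sample size, effect size or precision for RISRAS, so there is no figure to reproduce. The check compares the schedule with the planned analysis and then works through the arithmetic of levels and changes.

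**Scored occasions (sections 5.1, 5.3, 15)**

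| Instrument | Before RT | During RT | After RT |
|---|---|---|---|
| DLQI | 1 (Baseline) | 2 (Mid-Study, EndRT) | 1 (2-Week Post-RT) |
| RISRAS-Patient Symptom Scale | 0 | 2 (Mid-Study, EndRT) | 1 (2-Week Post-RT) |

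Two scores during RT give one difference, EndRT minus Mid-Study. Its starting point is not the same exposure for everyone: section 3.5 allows 15 to 40 fractions, so if the Mid-Study Visit falls halfway, it comes at about fraction 8 (15/2 = 7.5) for some subjects and fraction 20 (40/2) for others.

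**Scale ranges (section 5.3)**

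- Patient scale: 4 items scored 1 to 4, so 4 × 1 = 4 to 4 × 4 = 16.
- Professional scale: 4 items scored 0 to 4, so 0 to 4 × 4 = 16.
- RISRAS total: 4 + 0 = 4 to 16 + 16 = 32.

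**Illustration (all values assumed; none is in the documents)**

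Let a subject have b points above the floor before RT, constant through the study. Let the radiation reaction add m = 2 points by Mid-Study and e = 5 by EndRT.

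- Mid-Study score = 4 + b + m
- EndRT score = 4 + b + e
- Observable change = e − m = 5 − 2 = 3
- Change from before RT = e = 5
- Pre-existing share of the EndRT excess over the floor = b / (b + e)

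| b | Mid-Study | EndRT | Mid-Study to EndRT | Pre-RT to EndRT | Pre-existing share |
|---|---|---|---|---|---|
| 0 | 6 | 9 | 3 | 5 | 0/5 = 0% |
| 1 | 7 | 10 | 3 | 5 | 1/6 = 17% |
| 3 | 9 | 12 | 3 | 5 | 3/8 = 38% |
| 6 | 12 | 15 | 3 | 5 | 6/11 = 55% |

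The two effects are separate. The available change is 3 whatever b is, so stable pre-existing symptoms do not distort it; its fault is the 5 − 3 = 2 points of onset that it misses. The levels carry b in full, and so does the RISRAS total, since the patient score is added into it.

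**The case against.** The strongest reply is that the documents are consistent. Section 13.2 speaks of change during RT, not change from baseline, and that can be computed from Mid-Study and EndRT. This stands: the timing is a design choice, not a contradiction. The limitation is what that change can show.

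A reader might infer that pre-existing breast symptoms are counted as dermatitis in the planned changes. The arithmetic does not support this: if stable, they cancel. They matter only for levels and the total.

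A reader might also infer that RTOG and the professional scale share the fault. Both do start at Mid-Study, but RTOG is rated by the oncologist with grade 0 anchored as no change, which implies a pre-RT value of 0. The professional scale rates visible erythema, desquamation and necrosis, which the exclusions in section 3.6 make unlikely before RT.

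Those exclusions (active or chronic skin disease, infection, unhealed wounds, earlier trauma or scarring) also narrow the group with symptoms at entry. They do not empty it: section 3.5 expressly admits women after breast surgery, and the OnStudy Data Form records surgery before RT. The fourth item of the patient scale asks about interference from a skin reaction, so the argument rests on the other three.

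Baseline photographs, the baseline DLQI, weekly charting of skin changes and weekly questions about discomfort all exist. It would therefore be too strong to call the early phase unobserved. None of them supplies a reference value on this scale: the photographs have no scoring plan, and the DLQI measures effect on quality of life on a different range, 0 to 30.

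**Conclusion.** The point holds as a cheap improvement to an exploratory analysis. Symptom change on the patient scale can be measured only from mid-treatment, and pre-RT symptoms cannot be separated from dermatitis in the scale's levels or in the RISRAS total.

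The size cannot be fixed from the documents, which give neither the frequency nor the severity of symptoms before RT. The 2 missed points and the 0% to 55% range above follow from the assumed values and from the assumption that pre-existing symptoms stay constant.

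Three further inferences should not be drawn. The scale's floor of 4 is a constant and does no harm to trends or changes. The missing baseline does not lead to symptoms being attributed to the dressing: that judgement is made on the adverse event causality scale in sections 10.1 and 10.2, and without a control group a baseline score would not separate radiation from dressing effects either. And no conclusion on the primary or secondary endpoints is weakened.

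**What to change.** Add the four-item RISRAS-Patient Symptom Scale to the Baseline Visit, next to the DLQI. This means:

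- **Section 5.1:** list it among the Baseline Visit procedures, with the instruction adapted to the breast that is going to be covered by the dressing.
- **Section 5.3:** add Baseline to the scale's time points.
- **Section 15:** mark Baseline in the RISRAS-PSS row.
- **Section 13.2:** report the patient scale as change from baseline to Mid-Study, EndRT and 2-Week Post-RT, beside the levels.

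Scored occasions rise from 3 to 4, matching the DLQI. The cost is about one minute of subject time at a visit that must already take place before the first day of RT. No sample size changes.

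For subjects already enrolled without a baseline score, section 13.2 should state that change is measured from mid-RT and that levels may include symptoms present before treatment.

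No added RTOG or professional-scale rating is needed. It would require an oncologist visit after consent and before RT, which section 4.1 on remote consent shows is not guaranteed, and the grade 0 anchor and the exclusions leave little to gain.

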14. DATA HANDLING, CONFIDENTIALITY, AND STORAGE

All research data are specifically used for only research purposes and will contain the minimum personal identifiers required for the research. All written materials will be kept confidential, locked in the private office of the research coordinator and identified only by Subject Pair IDs (i.e., numbers) and initials. All data will be stored in a locked office in a locked cabinet and/or on a password-protected computer in a locked office. Results of the research may be presented at meetings or published for scientific purposes, but subject identification information will not be used. All of the forms listed below will be used in this study:

- Eligibility Checklist (paper)
- Screening Log (REDCap)
- Study Reimbursement Form (paper)
- W9 Form (paper)
- Withdrawal Form (REDCap)
- Comprehensive Study Log (password-protected Excel spreadsheet)
- OnStudy Data Form (REDCap)
- Silverlon® Compliance Log (paper)
- RTOG Scale (REDCap)
- RISRAS-Healthcare Professional

Assessment Scale (REDCap)

- RISRAS-Patient Symptom Scale (REDCap)
- Dermatology Life Quality Index (DLQI) (REDCap)
- EndRT Data Form (REDCap)
- Weekly AE/Chart Review Source Doc (REDCap)
- Questions Log (REDCap)
- 90-Day Phone Call Form (REDCap)
- Drug (Silverlon) Accountability Record (paper)

The majority of forms will be completed electronically. The Comprehensive Study Log are password-protected excel files only accessible by study personnel and will be stored in the study folder on the secure Dermatology CTU's sharedrive (i.e., smd drive). All other study forms will be electronic forms completed using REDCap. The patient and caregiver PROs will be completed via iPad and electronically stored in REDCap. All forms will be available in pdf format for completion on paper in case there are any issues with the electronic forms. Forms completed on paper will be kept confidential, locked in the private office of the research coordinator or the study PI.

Data Monitoring: The REDCap database will be audited monthly to ensure accurate data collection and entry. The PI will meet with study personnel weekly to discuss study accrual, study procedures, and data collection. No subject identifying data will be used. All of the written material will be kept confidential, locked in the private office of the principal investigator and identified only by Subject ID. At completion of the whole study (including final analyses), all

Page 35 of 41 RSRB STUDY00004587 Version Date: 09/14/2021 NCT04238728 paper forms will be destroyed.

Data Storage and Confidentiality: All measures completed on the iPad will be electronically stored in REDCap database at the University of Rochester Clinical & Translation Science Institute's (CTSI) secure REDCap data server, accessible only by [name] and assigned study personnel using their University-specific login and password. All completed paper questionnaires will be stored in study folders in a locked cabinet in Dermatology CTU or [name] office private locked office. All paper questionnaire data will be electronically entered into the REDCap database using an electronic data collection form. All forms will be coded by Subject Pair ID and Initials. The coding key will be stored electronically on the password-protected, encrypted, desktop computer connected to the University's secure server in [name] [name]'s office. The coding key will be stored for the length of the study and then permanently deleted at the completion of the study.

All data for this study is electronic and will be stored in the secure, study-specific, password-protected REDCap database or on the secure Dermatology CTU's University sharedrive. All paper documents will be stored in a locked file cabinet in Dermatology CTU or [name] the principal private office in the Department of Dermatology. Study personnel will have access to the study data. Statistical analyses will be performed on de-identified dataset containing Subject Pair IDs.

Study data, compliant with all HIPPA regulations, will be provided to the Sponsor (Argentum Medical) and BARDA teams assigned to this project. This will include individual and composite/analyzed data. All data will be electronic and can be shared with Argentum through encrypted email or other secure file sharing method (Box, Dropbox, etc.). Study data will be shared within the Argentum Research Team, and with the BARDA team assigned to this project. Composite data will be submitted to the FDA in support of a 510(k) application for additional indication of radiation dermatitis. FDA has the right to request access to the base or individual data.

All electronic and paper records and analysis will be retained for a period of 2 years following the date a marketing application is approved for the device (i.e., dressing) for the indication for which it is being investigated. If no marketing application is filed or if the application is not approved for such indication, data and records will be retained for a period of 2 years after the investigation is terminated or completed, or the date that the records are no longer required for purposes of supporting a premarket approval application. After the specified retention period, paper forms will be destroyed and the electronic records will be permanently deleted.

It is anticipated that the principal investigator, the Argentum research team, or both will publish results of this study in the peer-review literature. Protection of patient confidentiality will follow all standard rules in place for publication in the medical literature.

Page 36 of 41 RSRB STUDY00004587 Version Date: 09/14/2021 NCT04238728

15. SCHEDULE OF EVENTS AND DATA COLLECTION

Study Procedures	Screening	Baseline ²	Weekly During RT	Mid-Study RT	EndRT	2-Week Post-RT	90-Day Phone Call ⁶
Eligibility Checklist ¹	X						
Informed Consent ¹	X						
Reimbursement Form/W9		X					
OnStudy Data Form Log		X					
Silverlon® Accountability			Comple	eted as needed t	hroughout th	ne study	
Record			Compre	as needed i	inoughout ti	ie study	
Digital Photographs of Skin		X		X	X	X	
Radiation Oncologist:							
RTOG				X	X	X	
RISRAS-HPAS				X	X	X	
Patient PROs:							
Silverlon® Compliance Log ⁵		X	X	X	X	X	
DLQI		X		X	X	X	
RISRAS-PSS				X	X	X	
Screening Log ³			Comple	eted as needed t	hroughout th	ne study	
Comprehensive Study Log ⁴			Comple	eted as needed t	hroughout th	ne study	
Weekly AE/Chart Review			Х	X	X	X	
Source Doc			^	Λ	Λ	Λ	
Questions Log			X	X	X	X	
EndRT Data Form		X					
90-Day Phone Call Form				-			X
Withdrawal Form			Comple	eted as needed t	hroughout th	ne study	

¹Eligiblity Checklist and Informed Consent can be completed at same visit as the Baseline visit.

Page 37 of 41 RSRB STUDY00004587 Version Date: 09/14/2021 NCT04238728

²Baseline Visit can be performed at the same visit after informed consent is obtained. Baseline visit must be performed before the first day of radiation therapy.

³Screening Log will be completed to keep track of subjects that are approached about the study and decline or agree to participate in the study.

⁴The Comprehensive Study Log will keep track of subject's status during the study until study completion.

⁵A new Silverlon® Compliance Log will be given to the subjects every 7 days when new Silverlon® dressings are dispensed. The completed Silverlon® Compliance Log will be collected at this time.

⁶The 90-Day Phone call was requested by FDA to monitor subjects up to 90 days. The call will occur at 90 days after the start of radiation therapy. It is expected that any acute radiation-induced skin reactions will have recovered by this time.

